6.2 Subject Withdrawal from Study

6.2.1 Criteria for Subject Withdrawal from Study

A subject will be withdrawn from the study if any of the following conditions occur:

- 1) Development of intolerable severe adverse events or any condition that makes the subject unsuitable to continue participation in the study.
- 2) Occurrence of a severe allergic reaction related to the experimental vaccine, and the investigator assesses that the subject is no longer suitable to continue in the study.
- 3) The subject voluntarily withdraws from the study.

- 4) Poor compliance, failure to adhere to the study protocol, or loss to follow-up.
- 5) If an enrolled subject develops a condition during the study that makes continued participation unsuitable, and the investigator assesses that the risks of participation outweigh the potential benefits, the investigator may decide to withdraw the subject from the study.

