Secondary objective	To evaluate the immunogenicity and safety of humoral immune responses induced by recombinant zoster vaccine (CHO cells) in subjects aged 50 years and older.

Study Endpoints

Primary endpoints	The proportion of specific CD4+/CD8+ T cells activating at least two cytokines (TNF- α , IFN- γ , IL-2, CD40L) 30 days after full immunization.
Secondary endpoints	
Immunogenicity endpoints
 
 1. Geometric Mean Concentration (GMC) and seroconversion rate of anti-gE antibodies 30 days after full immunization; 2. Geometric Mean Fold Increase (GMFI) in anti-gE antibodies 30 days after the whole immunization course compared to pre-immunization (Day 0). 
Safety endpoints
 
 1. Incidence of solicited adverse events (AE) within 0-7 days after each dose, including local (injection site) and systemic (non-injection site) reactions; 2. Incidence of unsolicited AEs within 0-30 days after each dose; 3. Incidence of AEs within 30 minutes after each dose; 4. Incidence of adverse events of special interest (AESIs) from the first dose through 30 days after full immunization; 5. Incidence of serious adverse events (SAEs) from the first dose through 6 months after full immunization.

Study Design

Overall design	
Study design: Randomized, partially blinded
 
Immunization schedule: Experimental vaccine at 0 and 30 days; active control vaccine at 0 and 60 days

----------------	---

	
Study groups: Experimental group and control group
 
Blinding: LZ901-330 is a partially blinded study, with a double-blind design prior to the second dose, and an open-label design at the time of the second dose.
 
Number of subjects and groups
 
Approximately 300 subjects aged 50 and older will be enrolled and randomly assigned in a 1:1 ratio to the experimental group and the control group. The experimental group will receive two doses of the recombinant zoster vaccine (CHO cell), developed and manufactured by Beijing Luzhu Biotechnology Co., Ltd. / Luzhu Biopharmaceuticals (Zhuhai) Co., Ltd., with an immunization schedule of 0 and 30 days. The control group will receive two doses of the Recombinant Zoster Vaccine (RZV, ShingrixTM), products of GlaxoSmithKline Biologicals SA, with an immunization schedule of 0 and 60 days.
																							

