5.5.3.2 Unblinding Procedures

In this study, unblinding is required before the administration of the second dose, as the dosing intervals differ between the experimental group (30 days) and the control group (60 days). The unblinding process must be initiated by the principal investigator, who submits an unblinding request to the sponsor, and a record of the unblinding must be maintained.

In the event of group adverse events or study interruption for any reason, early unblinding may be conducted with the mutual agreement of the sponsor and the research team.

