6.2.2 Reasons for Subject Withdrawal

Subjects may discontinue their participation in the study at any time and for any reason. The investigator should inform subjects that they have the right to withdraw from the study at any time, and withdrawn subjects will not be replaced. Subjects who withdraw due to SAE/AE should be distinguished from those who withdraw for other reasons.

The investigator will follow up with subjects who withdraw due to SAE/AE until the issue is resolved.

If no study procedures, follow-ups, or further information collection occur from the date of withdrawal/last contact, the subject is considered to have "withdrawn" from the study. All data collected up to the withdrawal date/last contact will be used for analysis. The eCRF should record information related to the withdrawal, specifying whether the decision to withdraw was made by the subject or the investigator and indicating which of the following reasons led to the withdrawal:

- Serious adverse event (SAE)
- Non-serious adverse event (AE)
- Protocol deviation
- Withdrawal of informed consent (not due to an adverse event)
- Relocation from the study site
- Loss to follow-up
- Death
- Other (with detailed explanation)

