6.3 Discontinuation of Study Vaccine

A subject is considered to have discontinued the study vaccine if they do not receive the complete series of study vaccinations, meaning that from the date of discontinuation, they no longer receive any of the planned study vaccines. Subjects who discontinue the study vaccine are not necessarily withdrawn from the study. Depending on the circumstances, the investigator may arrange for them to continue completing other study procedures or visits as specified in the protocol (e.g., for safety or immunogenicity assessments).

Information related to early discontinuation of the study vaccine will be recorded in the eCRF. The investigator will document whether the decision to stop further vaccination/treatment was made by the subject or the investigator, along with the specific reason, which may include:

- Serious adverse event (SAE).
- Non-serious adverse event.
- Other (with specific details).

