8.5 Protocol Deviations

Protocol Deviations refer to any modifications or actions that do not follow the study
Study protocol/Version 1.1 /Date: Dec.8, 2023

protocol design or procedures without prior approval from the ethics committee. Actions that do not impact subject rights, safety, benefits, or the integrity, accuracy, and reliability of trial data, nor affect safety or primary endpoint evaluations, are considered protocol deviations. Actions that impact subject rights, safety, benefits, or the integrity, accuracy, and reliability of trial data, as well as those affecting safety or primary endpoint evaluations, are considered serious protocol deviations (protocol violations).

Examples of protocol deviations (including but not limited to):

- 1) Subjects did not sign the updated version of the informed consent form in a timely manner.
- 2) Storage and management of the study vaccine did not follow protocol requirements, or vaccine use was not confirmed as suitable before administration.
- 3) Diary cards and contact cards were not collected or distributed as required.
- 4) Other deviations.

Examples of protocol violations (including but not limited to):

- 1) Subjects entered the study without informed consent.
- 2) Subjects did not meet any inclusion criteria but were enrolled in the study.
- 3) Subjects met any exclusion criteria but were enrolled in the study.
- 4) Subjects did not receive the study vaccine according to the assigned vaccine allocation.
- 5) Vaccine dose, frequency, or administration route did not comply with protocol requirements.
- 6) Subjects used prohibited medications or those restricted by the protocol.
- 7) Subjects met withdrawal criteria but were not withdrawn from the study.
- 8) Other violations.

For protocol deviations/violations occurring during the study, site investigators must report the facts, process, cause, and impact of the event to the study responsible organization. The principal investigator or lead collaborative investigator should provide guidance on handling the event. Serious protocol deviations/violations must be reported to the ethics committee.

Researchers should provide targeted training for personnel involved in protocol violations to prevent recurrence and document the training process.

9. General Considerations: Regulatory, Ethical, and Trial Oversight

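### Section 6.2.1(4) requires withdrawal for undefined non-adherence, which does not fit sections 8.3, 8.5 and 5.1.9.2 and can end data collection for subjects with minor lapses

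*Protocol*

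**What the plan says.** Protocol section 6.2.1 opens with a mandatory rule: "A subject will be withdrawn from the study if any of the following conditions occur". Item 4 of the list, repeated in the synopsis, is "Poor compliance, failure to adhere to the study protocol, or loss to follow-up". Items 2 and 5 depend on an assessment by the investigator. Item 4 has no such qualifier, no definition of poor compliance and no threshold.

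Section 8.5 backs the rule with a sanction. Its examples of protocol violations, which it equates with serious deviations and requires to be reported to the ethics committee, include "Subjects met withdrawal criteria but were not withdrawn from the study".

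Section 6.2.2 lists protocol deviation among the reasons for withdrawal. It commits the investigator to further follow-up only for subjects who withdraw because of an AE or SAE, and it uses data collected up to withdrawal or last contact. It treats a subject as withdrawn "If no study procedures, follow-ups, or further information collection occur from the date of withdrawal/last contact".

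On blinding, section 5.5.3.2 states that "unblinding is required before the administration of the second dose".

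**The concern.** Non-adherence after randomization is normally recorded as a deviation and dealt with when the analysis sets are decided, while outcome collection goes on. Item 4 instead makes it a reason to end participation. The decision falls to the site, and from shortly before dose 2 the site knows the arm.

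Two outcomes are exposed. There is only one post-vaccination blood sample, 30 days after full immunization, so a subject withdrawn before it has no primary endpoint value. SAEs from the first dose to six months after full immunization are a safety endpoint, and a subject withdrawn in that period may have a truncated record. A sample that was never drawn cannot be recovered by any choice of analysis set.

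Loss could differ between arms. The sample falls at day 60 for LZ901 and day 90 for the control, so control subjects have longer in which to lapse. The Phase I adverse event rates quoted in section 3.2.3.1 were 30% for high-dose LZ901 and 100% for the control. Neither fact shows which way a bias would run.

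**Working it through.** The protocol gives no figure for withdrawals due to non-compliance, so the main check is to set the passages side by side.

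**How non-adherence is handled**

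| Place | Treatment of a lapse |
|---|---|
| 6.2.1(4) and synopsis | Withdrawal from the study, no threshold |
| 8.5, deviation examples | Diary or contact cards not collected or distributed as required: an ordinary deviation, by definition not affecting safety or primary endpoint evaluation |
| 8.5, violation examples | Restricted or prohibited medication: a violation, to be reported and followed by training; no withdrawal is mentioned |
| 8.5, violation item 7 | Not withdrawing a subject who meets the criteria is itself a violation |
| 8.3 | Major deviations affecting immunogenicity: exclusion from the per-protocol set at a blinded review before database lock, with earlier data still usable |

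Sections 8.3 and 8.5 assume that people who deviate remain in the study with data. Section 6.2.1(4), read with violation item 7, assumes that they leave.

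**What follow-up is stated after participation ends**

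- 6.2.2: AE/SAE withdrawals are followed until resolution.
- 5.5.3.3: after emergency unblinding the subject's participation ends, but safety follow-up continues.
- 6.2.1(4): nothing comparable is stated.
- 5.1.9.2: all SAEs to six months after full immunization are to be collected.

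**Who is affected, by time of withdrawal**

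1. *Before dose 2, with no second dose given.* The subject is outside both immunogenicity sets, because 8.3 requires completed vaccination for each. The added loss is the SAE record.
2. *After dose 2 and before the 30-day sample, for a major deviation.* The per-protocol set would exclude the subject anyway. The full analysis set loses a subject it could have kept, and SAE follow-up is lost.
3. *Same period, for a minor lapse.* The subject would have counted in both sets and now counts in neither. SAE follow-up is also lost. This is the main harm to the primary analysis.
4. *After the sample.* Only SAE follow-up is lost.

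In every case the subject stays in the safety set defined in 8.3 (any dose received), so an incomplete SAE record sits in the denominator as if it were complete.

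**The plan's own figure**

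Section 8.2 gives approximately 90% power with 135 evaluable per arm, one-sided alpha 0.025 and a 10-point margin. With power = Φ((pT − pC + 0.10)/SE − 1.96):

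- CD4+: SE = √((0.85×0.15 + 0.75×0.25)/135) = 0.0483; Φ(0.20/0.0483 − 1.96) = 98.5%.
- CD8+: SE = √((0.55×0.45 + 0.45×0.55)/135) = 0.0606; Φ(0.20/0.0606 − 1.96) = 91.0%.
- Both, if independent: 0.9854 × 0.9104 = 89.7%.

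The stated power is reproduced, and this point does not dispute it.

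**Scale only, on assumptions that the protocol does not supply**

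If a fraction w of one arm is removed and those removed respond g points less often than those retained, that arm's observed rate moves by w × g. Five of 150 at g = 20 gives (5/150) × 20 = 0.7 points. With w from 5% to 15% and g from 20 to 40, the shift is 1 to 6 points against the 10-point margin. It could favour either arm, depending on which arm loses subjects and whether they respond better or worse than the rest.

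**The case against.** The best defence is that the protocol, read as a whole, does not remove every deviator. Item 4 sits beside loss to follow-up and can be taken to mean sustained non-compliance. Section 8.5 answers ordinary lapses with reporting and training. Section 6.1.1 allows dose 2 to be postponed for listed reasons, so such a delay is not non-adherence, and 5.1.10.2 permits medication needed for an adverse event. This is a fair account of what was probably intended. It does not change the wording, and violation item 7 puts a site that reads item 4 leniently at risk of a reportable violation.

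Three stronger readings are tempting, and the protocol does not support them.

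- *That 6.2.2 forbids collection after withdrawal.* It describes a status: a subject with no further procedures or contact counts as withdrawn. It does not prohibit later collection. What is missing is any commitment to collect data after an item 4 withdrawal.
- *That 6.3 contradicts 6.2.1.* Section 6.3 says "Subjects who discontinue the study vaccine are not necessarily withdrawn from the study". That concerns stopping vaccine, whereas 6.2.1 concerns leaving the study, and both can hold. The real misfit is with 8.3, 8.5 and 5.1.9.2.
- *That sites could shape the primary result by removing non-responders.* Responder status comes from laboratory flow cytometry on the sample whose loss is at issue, so a site cannot select on it. Any bias would have to come through characteristics associated with both compliance and response.

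It is also correct that the per-protocol primary analysis would drop major deviators in any case, which limits the effect on the primary endpoint.

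**Conclusion.** The concern holds as an internal inconsistency with a practical consequence. A mandatory withdrawal rule without a threshold, enforced by violation item 7, does not fit the way 8.3 and 8.5 handle deviations or the SAE commitment in 5.1.9.2. Followed literally, it lets a site that knows the arm withdraw a subject for a lapse that would not have cost them their place in the per-protocol set.

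The harm falls mainly on subjects withdrawn for minor lapses before the 30-day sample, on the full analysis set and on the six-month SAE endpoint. How often item 4 would be invoked, in which arm and for subjects with what response are all unknown, so neither the size nor the direction of a bias can be computed. A reader might infer that the non-inferiority conclusion is compromised; the protocol does not support that. The conclusion rests on the literal wording and on the absence of any stated follow-up after an item 4 withdrawal.

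**What to change.** Reconcile 6.2.1(4), the matching synopsis entry, 6.2.2 and violation item 7 of 8.5 with 8.3, the deviation rules of 8.5 and 5.1.9.2:

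- State that non-adherence alone is recorded as a deviation and does not oblige the site to end data collection. Loss to follow-up can stay where it is.
- State that these subjects continue to the planned sample 30 days after full immunization, where vaccination was completed, and to the six-month SAE contact, unless consent is withdrawn or contact is lost.
- Narrow violation item 7 so that continuing this collection is not itself a violation.

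Whether dose 2 is given remains a matter for section 6.1 and is not addressed here.

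The cost is a wording amendment with ethics committee submission, and some effort in following poorly compliant subjects. Their visits and samples are already planned.

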6.2.2 Reasons for Subject Withdrawal

Subjects may discontinue their participation in the study at any time and for any reason. The investigator should inform subjects that they have the right to withdraw from the study at any time, and withdrawn subjects will not be replaced. Subjects who withdraw due to SAE/AE should be distinguished from those who withdraw for other reasons.

The investigator will follow up with subjects who withdraw due to SAE/AE until the issue is resolved.

If no study procedures, follow-ups, or further information collection occur from the date of withdrawal/last contact, the subject is considered to have "withdrawn" from the study. All data collected up to the withdrawal date/last contact will be used for analysis. The eCRF should record information related to the withdrawal, specifying whether the decision to withdraw was made by the subject or the investigator and indicating which of the following reasons led to the withdrawal:

- Serious adverse event (SAE)
- Non-serious adverse event (AE)
- Protocol deviation
- Withdrawal of informed consent (not due to an adverse event)
- Relocation from the study site
- Loss to follow-up
- Death
- Other (with detailed explanation)

6.3 Discontinuation of Study Vaccine

A subject is considered to have discontinued the study vaccine if they do not receive the complete series of study vaccinations, meaning that from the date of discontinuation, they no longer receive any of the planned study vaccines. Subjects who discontinue the study vaccine are not necessarily withdrawn from the study. Depending on the circumstances, the investigator may arrange for them to continue completing other study procedures or visits as specified in the protocol (e.g., for safety or immunogenicity assessments).

Information related to early discontinuation of the study vaccine will be recorded in the eCRF. The investigator will document whether the decision to stop further vaccination/treatment was made by the subject or the investigator, along with the specific reason, which may include:

- Serious adverse event (SAE).
- Non-serious adverse event.
- Other (with specific details).

6.4 Loss to Follow-Up

Loss to follow-up refers to a situation where a subject, for any reason, is unable to continue through to the final follow-up visit as required by the study protocol. The investigator will attempt to contact subjects who do not return for scheduled visits or follow-up.

6.5 Criteria for study suspension

- 1) New data regarding the study vaccine obtained from this study or any other study, or management reasons suggesting that the risks outweigh the benefits, prompting the sponsor, investigator, and/or ethics committee to recommend a suspension;
- 2) The occurrence of a serious adverse event that is potentially life-threatening or leads to the subject death, which may be related to the vaccination;
- 3) If $\geq 15\%$ of subjects experience Grade 3 or higher adverse events during the study, and these events do not resolve to below Grade 3 within 48 hours.

If the study is suspended, the ethics committee (IRB) and provincial or national drug regulatory authorities or relevant departments must be notified. An expert meeting will be convened to assess safety, and a blinded analysis may be conducted if necessary to determine whether the study should continue. The study may resume once safety, protocol compliance, and data quality issues are resolved and the requirements of the sponsor, ethics committee, and/or national regulatory authorities are met.

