SOP	Standard Operation Procedure
SS	Safety Set

Abbreviation	Expanded Term
SUSAR	Suspected Unexpected Serious Adverse Reaction
TEAE	Treatment Emergent Adverse Event
VZV	Varicella Zoster Virus
WHODD	WHO Drug Dictionary
ZBPI	Zoster Brief Pain Inventory

Definitions of Terms

Month	30 days.
Women of Childbearing Age	Women from menarche until menopause are considered capable of childbearing unless it has been clearly confirmed that they have undergone a hysterectomy, bilateral salpingectomy, and bilateral oophorectomy.
Severe Medical History	Diseases requiring emergency treatment, hospitalization, and/or surgical procedures.
Antibody Positivity Rate and Antibody Seroconversion Rate	1) Abnormal antibody concentration (measured by ELISA): Specific anti-gE antibody concentration >0.1 IU/mL (or 100 mIU/mL) is defined as positive. 2) Pre-immunization antibody positivity rate: The proportion of subjects with anti-gE antibody positivity in pre-immunization serum samples. 3) Post-immunization antibody concentration ≥ 4 times the pre-immunization level is defined as seroconversion. 4) Seroconversion rate: The proportion of subjects achieving seroconversion in post-immunization serum samples.
Antibody Fold Increase	The fold increase in specific anti-gE antibody concentration (measured by ELISA) compared to the pre-immunization level.
HZ Suspected Cases	Suspected herpes zoster (HZ) cases meet at least one of the following criteria: a) Unilateral pain or rash. b) Dermatomal, unilateral distribution of grouped vesicles on an erythematous base. c) Neuralgia.

Protocol Synopsis

Study title	A randomized, blinded clinical trial to evaluate the immunogenicity and safety of the recombinant zoster vaccine (CHO cells) LZ901 compared with a similar active vaccine in subjects aged 50 years and older
Sponsor	Beijing Luzhu Biotechnology Co., Ltd. Luzhu Biopharmaceuticals (Zhuhai) Co., Ltd.
Protocol No.	LZ901-330, V1.1
Study phase	III+
Study vaccine	Recombinant zoster vaccine (CHO cells) (LZ901) Recombinant Zoster Vaccine (RZV, Shingrix™)
Indications	To prevent herpes zoster (HZ) and its complications caused by Varicella-Zoster Virus (VZV) infection.

Study Objectives

Primary objective	To evaluate the immunogenicity of cellular immune response induced by recombinant zoster vaccine (CHO cell) in subjects aged 50 years and older, in comparison to the active control vaccine.

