Criteria for suspension and termination of the study	
Criteria for study suspension:
 
 1. New data regarding the study vaccine obtained from this study or any other study, or management reasons suggesting that the risks outweigh the benefits, prompting the sponsor, investigator, and/or ethics committee to recommend a suspension; 2. The occurrence of a serious adverse event that is potentially life-threatening or leads to the subject death, which may be related to the vaccination; 3. If $\geq 15\%$ of subjects experience Grade 3 or higher adverse events during the study, these events do not resolve to below Grade 3 within 48 hours. 
If the study is suspended, the ethics committee (IRB) and provincial or national drug regulatory authorities or relevant departments must be notified. An expert meeting will be conducted to assess safety, and a blinded analysis may be conducted if necessary to determine whether the study should continue. The study may resume once safety, protocol compliance, and data quality issues are resolved and the requirements of the sponsor, ethics committee, and/or national regulatory authorities are met.
 
Criteria for study termination:
 
 (1) Reaching the study endpoints; (2) Any subject experiencing a life-threatening or fatal serious adverse event

	
related to the study vaccine during the study;
 
(3) The study meets the criteria for suspension ($\geq 15\%$ of subjects experience \geq Grade 3 adverse events, and these do not resolve to below Grade 3 within 48 hours), and it is determined that these events are related to the study vaccine.
 
If the study is terminated early, the sponsor will immediately notify the investigator, clinical trial institution, ethics committee, and regulatory authorities of the reason for termination in accordance with the relevant regulatory requirements. The investigator should report to the clinical trial institution and IRB, providing a detailed written explanation.
 
Regardless of the reason for suspension or termination, the investigator must immediately inform the subjects and ensure appropriate follow-up is conducted.

Study period	Duration of participation for each subject: From the first visit to the final visit, each subject is expected to participate in the study for approximately 7 to 8 months.

Schedule of Activities

Visit	V1	V2	V3	V4	V5	V6	V7	V8

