5.4 Preparation, Handling, Storage, and Counting

5.4.1 Preparation of Study Intervention

The preparation and administration of both the study vaccine and the control vaccine will be carried out by authorized medical personnel who are not involved in the clinical assessment. The study vaccine is a ready-to-use liquid formulation intended for direct injection.

The control vaccine preparation follows the manufacturer instructions. The AS01B

adjuvant is mixed with the lyophilized varicella-zoster virus glycoprotein E (gE) antigen component from a single-dose vial to prepare the injectable suspension. After mixing, the final dose of the control vaccine is 0.5 mL per single administration.

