6.6 Criteria for study termination

- (1) Reaching the study endpoints;
- (2) Any subject experiencing a life-threatening or fatal serious adverse event related to the study vaccine during the study;
- (3) The study meets the criteria for suspension ($\geq 15\%$ of subjects experience \geq Grade 3 adverse events, and these do not resolve to below Grade 3 within 48 hours), and it is determined that these events are related to the study vaccine.

If the study is terminated early, the sponsor will immediately notify the investigator, clinical trial institution, ethics committee, and regulatory authorities of the reason for termination in accordance with the relevant regulatory requirements. The investigator should report to the clinical trial institution and IRB, providing a detailed written explanation.

Regardless of the reason for suspension or termination, the investigator must immediately inform the subjects and ensure appropriate follow-up is conducted.

7. Study Evaluation and Procedures

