7.3.3 Safety Assessment

The safety analysis cohort will include all subjects who meet the following criteria:

- Have received at least one dose of the study vaccine or control vaccine according to randomization;
- Have sufficient data for safety analysis (at least one dose and follow-up for safety);
- Have not received other prohibited medications or vaccines per protocol. For detailed information on the safety follow-up time and content, please refer to Section 5.1.9.

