8.3 Analysis Sets

Full Analysis Set (FAS): This includes all subjects in both the experimental vaccine group and the similar active control vaccine group who follow the intention-to-treat (ITT) principle. Subjects must have been randomized, completed vaccination, and have baseline and at least one post-immunization immunogenicity result. For subjects with vaccination number errors, immunogenicity evaluation will follow the original randomized group.

Per-Protocol Set (PPS): This set includes all subjects in the experimental and active control vaccine groups who meet inclusion/exclusion criteria, are randomized, complete vaccination, and have baseline and 30-day post-full immunization immunogenicity results. Subjects with major protocol deviations impacting immunogenicity evaluation will be excluded, though data prior to deviations may still be included in the analysis.

Safety Set (SS): This includes all subjects who received any dose of the vaccine.

Safety analyses for each dose will be based on the actual number of subjects who received each dose. Specifically: The first-dose safety set includes all randomized subjects who received the first dose of the study vaccine. The second-dose safety set includes all randomized subjects who completed the second dose of the study vaccine.

Safety analyses for each dose will follow the ASAT (All Subjects As Treated) principle, analyzing subjects based on the vaccine group they actually received.

The determination of the above analysis sets will occur in a blinded data review meeting before database lock, with input from the primary investigator, sponsor, statisticians, and data managers.

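### The 15% stopping limit pools both groups, so the comparator can mask an LZ901 excess; comparator events alone can also reach it, with an ambiguous result under 6.6(3)

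*Protocol*

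**What the plan says.** Section 6.5(3) suspends the trial at a limit of 15% or more, counted as the share "of subjects experience Grade 3 or higher adverse events during the study". A second condition concerns duration: "these events do not resolve to below Grade 3 within 48 hours". The synopsis has the same rule. Neither place names a group or says whether the 15% is taken of planned, enrolled or dosed subjects. Under 6.5, a suspension leads to an expert meeting and, if needed, a blinded analysis, and the trial may resume.

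Section 6.6(3) terminates the trial if the same limit is met "and it is determined that these events are related to the study vaccine". Section 6.6(2) terminates on one life-threatening or fatal serious adverse event related to the same vaccine.

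The term *study vaccine* has two meanings:

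- **Both products.** The synopsis entry lists "Recombinant zoster vaccine (CHO cells) (LZ901) Recombinant Zoster Vaccine (RZV, Shingrix™". Section 8.3 says "The first-dose safety set includes all randomized subjects who received the first dose of the study vaccine", which covers both groups.
- **LZ901 only.** Section 5.4.1 speaks of "both the study vaccine and the control vaccine", and 7.3.3 has "Have received at least one dose of the study vaccine or control vaccine according to randomization".

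The first-dose period is double-blind. Section 5.5.3.2 says "unblinding is required before the administration of the second dose", because the second dose falls at day 30 for LZ901 and day 60 for the comparator.

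**The concern.** This is the only suspension or termination criterion with a numeric threshold, and it is applied while dosing continues. It therefore belongs in the protocol.

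The trial has one investigational product and one licensed comparator, in equal numbers. A limit on the pooled count gives the investigational product no limit of its own. If LZ901 caused persistent severe reactions well above 15% and the comparator caused few, the pooled share could stay below 15% to the end.

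The opposite case is also unresolved. Enough comparator events would suspend the trial on their own. Under one meaning of *study vaccine*, related comparator events then terminate it; under the other they do not. Section 6.6(2) has the same problem, and there a single event is enough.

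**Working it through.** **Inputs from the protocol.** Limit 15% (6.5(3)); 300 subjects randomised 1:1, so 150 per group (5.5.1). The 15% comes with no derivation, so there is no figure to reproduce.

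**Assumed inputs.** The protocol gives no rate of Grade 3+ events lasting beyond 48 hours for either vaccine. The nearest figure is 2.01% Grade 3 events of any duration in the Phase II high-dose group (1.2.2). The rates below are illustrations. Subjects are taken as independent.

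**Step 1: counts needed.**
- Pooled: 0.15 × 300 = 45.
- One group: 0.15 × 150 = 22.5, so 23 (23/150 = 15.3%).
- All events on LZ901, none on the comparator: 45/150 = 30% on LZ901 to reach the pooled limit. An LZ901 group at 23 of 150 gives a pooled share of only 23/300 = 7.7%.

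**Step 2: chance of reaching the limit at the final count.** Let X ~ Bin(150, p_LZ901) and Y ~ Bin(150, p_comparator). The pooled rule is P(X + Y ≥ 45); the LZ901 rule is P(X ≥ 23).

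| LZ901 rate | Comparator rate | Expected pooled count | Pooled, 45/300 | LZ901 group, 23/150 |
|---|---|---|---|---|
| 20% | 2% | 30 + 3 = 33 | 0.016 | 0.94 |
| 25% | 2% | 37.5 + 3 = 40.5 | 0.23 | 0.999 |
| 10% | 10% | 15 + 15 = 30 | 0.004 | 0.026 |
| 2% | 30% | 3 + 45 = 48 | 0.72 | <0.001 |

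The first two rows show the dilution. The last row shows that comparator events alone can meet the pooled limit while LZ901 is at 2%.

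**Step 3: what 6.6(3) does in the last row.** Suppose the comparator events are judged vaccine-related. With *study vaccine* in the sense of the synopsis and 8.3, the trial terminates. In the sense of 5.4.1 and 7.3.3, it does not. Section 6.2.1 uses a separate term, experimental vaccine, for a severe allergic reaction to LZ901, so an unambiguous term was available.

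**Step 4: an LZ901 check from 50 subjects on.** Threshold ceil(0.15n), looked at after every LZ901 subject from n = 50 (8 events) to n = 150 (23 events), by exact recursion. Probability of calling a meeting:
- 2% true rate: <0.001
- 5%: 0.006
- 10%: 0.23
- 20%: 0.98

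**The case against.** **Pooling is the natural count under the blind.** In the double-blind period no other count is available without an unblinded role. This stands, and is why the pooled criterion should stay. It does not explain why no LZ901 count follows once allocation is opened for dose 2.

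**Other brakes exist.** Sections 6.5(1), 6.5(2), 5.5.3.2 and 7.4.6 allow action on judgement, suspension is reversible, and termination needs a separate finding of relatedness. This also stands. Subjects are not unprotected, and no endpoint or error rate is affected.

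**Both products is the ordinary sense of *study vaccine*.** This is arguable: the synopsis and the per-dose safety sets support it. But 7.3.3 is itself a safety section and uses the other sense. If both products are meant, ending the trial because of a licensed comparator should be a stated decision.

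Two stronger readings are tempting and are not supported.

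- *The missing denominator by itself makes the rule erratic, since one affected subject among the first six is 16.7%.* If every 48-hour outcome is assumed known at once, a running count with no minimum trips with probability 0.12 at 2% in both groups and 0.72 at 20% against 2%. But persistence takes 48 hours to establish, Diary Cards are reviewed at day 7, and 3.1.4 gives the whole study 7 to 8 months, when one control subject needs 60 days plus 6 months. Enrolment must therefore be fast. With an assumed 3-day delay and 5 to 10 subjects dosed per day, the figures fall to <0.001 and about 0.03 to 0.16. The denominator is largely a missing detail, and these figures do not justify a mandatory minimum number, which would weaken early protection.
- *A comparator-driven trip is the likelier one.* Section 3.2.1 stresses how often the comparator causes side effects, but 3.2.3.1 reports Phase I events as mainly Grade 1 and resolving on their own, with a 100% event rate on the comparator. Frequency is not severity or persistence, and the protocol gives no rate that ranks the two cases.

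**Conclusion.** The concern holds for pooling and for the term *study vaccine*. A single pooled 15% limit is a weak guard against an LZ901 excess: at an assumed 20% against 2%, the final count reaches it in 1.6% of trials, against 94% for the same percentage applied to LZ901. That comparison rests on assumed rates, independent subjects and a count at full enrolment. The 30% needed on LZ901 when the comparator has no events is arithmetic and needs no assumed rate.

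The two senses of *study vaccine* follow directly from the text and leave 6.6(2) and 6.6(3) undecided for comparator events. The denominator should be stated, as a minor completion. The change is worth making because it is cheap and adds a safety check on the investigational product; it is not a flaw that puts the trial's conclusions in doubt.

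**What to change.** 1. In 6.5(3), 6.6(3) and the synopsis, keep the pooled criterion and state that its denominator is all subjects dosed to date.
2. Add to 6.5: once allocation is opened before dose 2 (5.5.3.2), tally the same events by group. If at least 15% of 50 or more LZ901 subjects are affected, convene the expert meeting that 6.5 already provides for.
3. In 6.6(2) and 6.6(3), replace *study vaccine* with the named product or products, so that it is clear whether events due to the licensed comparator alone terminate the trial.

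**Cost.** Wording in three places and one tally. No unblinded role is added in the double-blind period. The LZ901 check can start only at about day 30, so it mainly protects dose 2; with fast enrolment few first doses would remain. Looked at after every subject from 50 to 150, it calls an unneeded meeting with probability about 0.006 at a true 5% rate and 0.23 at 10%. If enrolment is already complete when it starts, so that it is in effect one look at 150, the 10% figure is 0.026. A false call costs a meeting and does not stop the trial. The starting number of 50 is a choice the sponsor may vary.
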